7 SAFETY MANAGEMENT

7.1 Risks to Human Subjects

The placement of the esophageal balloon catheter in carefully selected patients (see exclusion criteria above) confers a relatively small risk to the patient (such as trauma to the nasopharynx, esophageal irritation, stimulation of cough or vomiting). Adverse events possibly related to mechanical ventilation and PEEP titration will be defined as new development of pneumothorax and hypotension thought to be related to changes in mechanical ventilation. Despite these theoretical concerns, no adverse effects were seen in a small randomized trial using an esophageal balloon to titrate to optimal PEEP in patients with ARDS. (5)

7.2 Data and Safety Monitoring Plan

All participants will be continuously monitored by critical care nurses under the guidance of critical care physicians per individual ICU protocols.

Stopping rules and procedures

Subject stopping rules will be the development of any of the following after randomization:

- New pneumothorax
 - Pneumothorax is a known risk factor for all patients requiring mechanical ventilation with a case rate of <1% of all mechanically ventilated patients. In previous studies of optimal PEEP determination using esophageal balloon-guided pressure measurement, no pneumothoraces were observed. We believe the study procedures will be safe for both arms, and that the intervention arm will be at lower risk for this outcome. However, development of a pneumothorax will necessitate a chest tube and will invalidate the measurement of pleural pressure. Therefore the study procedures must be stopped.
- Epistaxis requiring intervention
 - In the event of epistaxis requiring packing or intervention, the esophageal balloon will be removed and the study subject's participation in the study will end.
- Hypotension
 - In the event a patient experiences a drop in mean arterial pressure (MAP) below 65 mm Hg or a significant change in vasoactive medication requirement (>10 mcg/min dose of norepinephrine equivalent), that is felt by the clinical ICU team to possibly be related to the intervention, the study subject's PEEP will be dropped by 2 cm H₂O every 5 minutes until the parameter returns to an acceptable range (as determined by the clinical ICU team) or until the PEEP reaches the pre-intervention level. The patient will remain on no higher than this new PEEP for the remainder of the study.

Adverse Event Reporting

All Adverse Events will be documented and graded using CTCAE grading, defined as any patient who develops one of the following (by CTCAE grading):

- grade 3-5 hypotension
- grade 2-5 pneumothorax
- grade 2-5 epistaxis

Screening for possible adverse events will occur daily. Each possible adverse event will be reviewed by a UNC critical care physician, independent of the study, within 72 hours of occurrence. The primary independent reviewer will be [name], MSCR; if he is on clinical service responsible for the study subject, then [name], PhD will serve as the independent reviewer. After independent review, events considered to be probably or definitely related to the intervention will be submitted to the IRB for review. In addition, we will utilize a Data and Safety Monitoring Board to review aggregate safety data.

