Safety Evaluations	Periodic review will be performed by the NC TraCS DSMB. They will review aggregate safety data after 25, 50, and 75% enrollment to ensure there are not safety differences between the groups in hypotension requiring vasopressors and development of pneumothorax. All patients will have

continuous monitoring of HR, BP, and oxygenation per ICU protocol to monitor patient safety.

Statistical And Analytic Plan

This is a randomized, controlled trial to evaluate the effect of using Optimal PEEP based on an esophageal balloon measurement on duration of mechanical ventilation. We hypothesize that using Ptp to identify optimal PEEP will reduce time on the ventilator and therefore increase the ventilator free days at day 28. The primary outcome is the number of ventilator-free days, defined as the number of days alive and ventilator-free by day 28. Differences between the two groups in the primary outcome will be analyzed using independent t-tests and a linear regression model adjusting for BMI, abdominal girth, and Ptp.

DATA AND SAFETY MONITORING PLAN

The PI will be responsible for maintaining patient data and ensuring accuracy of the data collected. All patient data will be collected using REDCap through the NC TraCS system. REDCap allows for immediate data validation and range setting to reduce the likelihood of erroneous data entry. Data created for analysis will be de-identified and secured on a password protected UNC School of Medicine network hard drive. All investigators will be trained on completing the electronic case report form.

Patient safety will be monitored with continuous cardiovascular monitoring by the critical care team. Subject stopping rules will be in place to end the study intervention, including refractory hypotension, development of pneumothorax, or changes in oxygenation or hemodynamics that the primary team feels may be related to changes in PEEP.

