4.4 Participant Completion/ Withdrawal

Participants will complete the study at the time of death or the conclusion of 28 days, whichever occurs first.

Early completion of the trial for each participant will occur if any of the following outcomes are met:

- a. Patient or family withdraw consent for the study
- b. The clinical team feels that the patient no longer meets appropriateness for the study
- c. Patient develops an adverse effect felt possibly related to the intervention (refractory hypotension, nasopharyngeal bleeding, pneumothorax, etc)

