5 STUDY EVALUATIONS AND MEASUREMENTS

5.1 Measurements

Procedures for PEEP and FiO2 Titration

Both groups will have their FiO2 titrated based on results of the PaO2 from an arterial blood gas, if available, or SpO2 values if no arterial blood gas is obtained. PEEP titration will vary by group as below.

Setting PEEP in Intervention Group

The waveforms of Paw, Pes, and Ptp will be visualized on the ventilator. Ptp is obtained from Paw – Pes. PEEP will be increased on the ventilator to achieve a Ptp between 0 and +2 cm H₂O (Optimal PEEP). Measurements will be obtained daily and adjustments to PEEP will occur daily. PEEP will be reduced below Optimal PEEP in the setting of hemodynamic compromise (requiring increasing vasoactive medications for blood pressure support).

Setting PEEP in Control Group

PEEP in the control group will be determined by High PEEP ARDSnet PEEP/FiO₂ table. Titration of PEEP will occur when clinically indicated by PaO₂ or SpO₂, and FiO₂. We chose the High PEEP table based on the clinical suspicion that obese patients may require higher PEEP levels on average than non-obese patients to balance the additional pressure of their chest wall. In addition, EPVent2, a study of esophageal balloon PEEP titration in patients with ARDS utilized the High PEEP table. Patients with moderate and severe ARDS benefit from higher levels of PEEP. (8)

Procedures for Assessment of Readiness for Extubation

Both groups will have a daily assessment of readiness for extubation performed by the Respiratory Therapist and bedside RN according to the standard clinical protocol. Criteria for both groups to undergo a spontaneous breathing trial (SBT) will be the following:

- 1) Not in prone position
- 2) No increased ICP
- 3) No active seizures
- 4) No alcohol withdrawal requiring escalating treatment
- 5) No active myocardial ischemia in discussion with nursing or physician
- 6) No unstable spine fractures
- 7) No free muscle flaps
- 8) FiO₂ ≤ 50% and SpO₂ ≥ 90%
- 9) Minute Ventilation < 15 L/min
- 10) Minimal vasopressors (norepinephrine < 5mcg/min or 0.05 mcg/kg/min, dopamine/dobutamine ≤ 5 mcg/kg/min)
- 11) HR < 140
- 12) RR ≤ 35
- 13) SBP > 90 and < 180

Failure of an SBT will be demonstrated if any of the following criteria are met:

- 1) SpO₂ < 90% sustained ≥ 5 minutes
- 2) Spontaneous VT ≤ 4ml/kg IBW – sustained ≥ 5 minutes
- 3) Respiratory Rate ≥ 35/min
- 4) Rapid Shallow Breathing Index >105

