- 5) Other signs of respiratory distress (distress = 2 or more)
- 6) HR > 140
- 7) Marked accessory muscle use
- 8) Abdominal paradox (belly breathing)
- 9) Diaphoresis

Failure of an SBT will be determined by the bedside RT based on current policy (PolicyStat ID: 4745433). If a patient fails an SBT, they will be returned to their previous ventilator settings until the next daily assessment. If the patient tolerates a 30-minute SBT, they will be returned to their previous ventilator settings for 60 minutes, then extubated to an appropriate oxygen delivery device. Ventilator settings during the SBT and extubation procedures will vary between groups as below. Blinding of the respiratory therapist determining eligibility for SBT to treatment arm will not be possible because of the differences between SBT protocols. However, the study team will make no determinations of readiness for extubation. If a member of the study team is on service during the time of potential enrollment, these patients will be excluded to avoid bias.

SBT and Extubation Procedure for Intervention Group

Patients in the Intervention group will undergo an SBT regardless of their PEEP level. The PEEP that generates a Ptp of 0 will be considered their optimal PEEP, and this will not be lowered for the SBT. The Intervention Group SBT will consist of a trial of a pressure support of 5 cm H₂O and Optimal PEEP.

SBT and Extubation Procedure for Control Group

Patients in the Control group will undergo an SBT **when they reach a PEEP \leq 8 cm H₂O**. This is the current standard of care based on the SBT protocol at UNC Hospitals. SBT and extubation prior to meeting these criteria will be based on primary medical team's discretion and will be recorded for analysis and safety tracking.

Procedures for ventilator weaning after tracheostomy

Any patient who fails to be eligible for extubation or fails extubation will be eligible for tracheostomy per usual unit protocol. The study team will play no part in the decision to proceed with tracheostomy for ventilator weaning. After tracheostomy, it is routine practice to forego SBT and proceed with trials of liberation from the ventilator with oxygen delivered by an aerosol tracheostomy collar ("trach collar trials" or TCT). The same criteria are used to perform a TCT as an SBT above. The two groups will have different approaches to TCT.

TCT Procedure common to both groups

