6 STATISTICAL CONSIDERATION

6.1 Primary Endpoint

The primary outcome is the number of ventilator-free days (VFD), defined as the number of days alive and ventilator-free by day 28. The assessment of the primary outcome will be conducted by a study team member after subject completion in the study. In order to minimize potential bias, this team member will be blinded to treatment arm assignment.

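### For PEEP-related hypotension, section 7.2 caps PEEP and keeps the patient in while the synopsis ends the intervention, and a patient capped below the PEEP giving Ptp 0 cannot also follow the intervention SBT rule

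*Combined protocol and SAP*

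**What the plan says.** Five places in the combined protocol and SAP bear on the same event.

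- **7.2, stopping rules.** The list opens "Subject stopping rules will be the development of any of the following after randomization", and hypotension is on it. The trigger is a mean arterial pressure below 65 mm Hg, or a vasoactive change above 10 mcg/min of norepinephrine equivalent, that the ICU team thinks may be due to the intervention. PEEP then comes down by 2 cm H₂O every 5 minutes until the parameter is acceptable "or until the PEEP reaches the pre-intervention level". After that, "The patient will remain on no higher than this new PEEP for the remainder of the study". By contrast, epistaxis needing intervention ends participation and pneumothorax stops study procedures.
- **Synopsis, Data and Safety Monitoring Plan.** "Subject stopping rules will be in place to end the study intervention, including refractory hypotension, development of pneumothorax, or changes in oxygenation or hemodynamics", where the primary team thinks those changes may come from PEEP.
- **4.4(c).** Early completion of the trial occurs if "Patient develops an adverse effect felt possibly related to the intervention (refractory hypotension, nasopharyngeal bleeding, pneumothorax, etc" applies.
- **5.1, setting PEEP in the intervention group.** "PEEP will be reduced below Optimal PEEP in the setting of hemodynamic compromise (requiring increasing vasoactive medications for blood pressure support". The same rule stands in 1.2.
- **5.1, intervention-group SBT.** "The PEEP that generates a Ptp of 0 will be considered their optimal PEEP, and this will not be lowered for the SBT". The trial is run at pressure support 5 cm H₂O plus that PEEP, and no exception is given.

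On the outcome, 3.1 states 28-day follow-up for ventilator-free days and 5.2 takes the outcome from the EMR. Section 6.1 adds: "The assessment of the primary outcome will be conducted by a study team member after subject completion in the study". Section 6.2 says that missing values are left out.

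**The concern.** Hypotension is one of the two PEEP-related harms that the protocol itself names in 7.1. In an open-label trial at two sites, bedside staff need one answer when it happens. As written, the same patient could stay in the intervention arm at a capped PEEP or have the intervention ended. If the hypotension is called refractory, the patient could be completed early.

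The choice reaches the primary outcome by two routes. First, the SBT is the usual path to extubation and so to ventilator-free days, and the PEEP at which a capped patient is tested is unclear. Second, if early completion leads to a missing ventilator-free-day value, the patient drops out of the primary t-test because of an event that the treatment may have caused.

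**Working it through.** **The plan's own figures, for background.** Inputs from 6.3 and 6.2: SD 2.9 days, power 80%, two-sided alpha 0.05. The two-sample t-test solution is 15.69 per group for a 3-day difference, so 16, and 33.99 for a 2-day difference, so 34. With 10% dropout, 34/(1 − 0.10) = 37.8, so 38 per group and 76 in total. All stated figures reproduce, and this point does not dispute them.

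**Step 1: one event, side by side.** Take a patient whose mean arterial pressure falls below 65 mm Hg, who is thought possibly to be reacting to PEEP, and who recovers on step-down.

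| Place | Does the rule reach this patient? | Consequence |
|---|---|---|
| 7.2 | Yes | Step-down, cap, stays in |
| 1.2 and 5.1 | Yes, if vasoactive drugs are rising | PEEP below Optimal PEEP, intervention continues |
| Synopsis | Yes: its last trigger is any PEEP-related hemodynamic change, not only refractory cases | Intervention ends |
| 4.4(c) | Unclear: the hypotension it names is refractory, but the list is open-ended | Early completion, if it applies |

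The direct conflict is between 7.2 and the synopsis. If the patient does not recover, 7.2 stops the step-down at the pre-intervention PEEP and says nothing further. Section 4.4(c) then seems meant to apply, but no section defines refractory. Section 7.3 uses the word for a DSMB suspension trigger (2 of 10, or 20% once more than 10 are enrolled) and refers to the CTCAE criteria in 7.2, where hypotension is grade 3 to 5. It does not equate the term with a grade.

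**Step 2: when the cap meets the SBT rule.** At end-expiration, Ptp = PEEP − Pes. Let f be the share of a PEEP change that passes to Pes (assumed 0 to 0.5; the documents give no value). Each 2 cm H₂O step lowers Ptp by 2 × (1 − f). The starting range is 0 to +2 cm H₂O.

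| Steps | f = 0 | f = 0.5 |
|---|---|---|
| 1 | −2 to 0 | −1 to +1 |
| 2 | −4 to −2 | −2 to 0 |
| 3 | not needed | −3 to −1 |

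So two steps (f = 0) or three (f = 0.5) put every such patient below Ptp 0, provided the pre-intervention floor is low enough to allow them. There is no conflict for a patient who steps from +2 to exactly 0, whose floor already gives Ptp 0 or more, or whose Ptp-0 PEEP later falls to the cap. SBT entry requires norepinephrine below 5 mcg/min or 0.05 mcg/kg/min. That delays the conflict but does not remove it, because the cap outlasts the hypotension.

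**Step 3: the analysis.** Suppose k₁ intervention and k₀ control patients are completed early with missing values, and their ventilator-free days would have been d₁ and d₀ lower than those of the rest of their arm. With 38 per arm, each arm's mean is overstated by k × d/38, and the bias in the difference is (k₁d₁ − k₀d₀)/38. The documents give none of these four quantities. For the form only: with k₀ = 0, k₁ from 1 to 4 and d₁ from 3 to 14, the result runs from 1 × 3/38 = 0.08 to 4 × 14/38 = 1.47 days. These are assumed inputs, not estimates. A d of 14 is 14/2.9 = 4.8 of the plan's SDs, so the top of the range carries no weight.

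**The case against.** The best defence is a graded reading. Sections 1.2, 5.1 and 7.2 all lower PEEP for hemodynamic compromise, while the synopsis and 4.4(c) name refractory hypotension, which suggests that stopping is kept for cases that do not respond. A cap below the target largely does end the intervention, and a cap lasting to the end of the study can be read as covering the SBT too. Missing data after early completion is a general matter, and 3.1 with EMR outcomes makes a missing value avoidable.

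Much of this stands. The graded reading fits 4.4(c). It does not fit the synopsis, whose last trigger has no refractory limit. Reading the cap as overriding the SBT rule is sensible, and the fix adopts it, but 5.1 forbids lowering PEEP for the SBT and gives no exception.

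A reader might infer more than the documents support:

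- *That 4.4(c) removes every patient who meets the 7.2 trigger.* It names only refractory hypotension.
- *That such losses occur only in the intervention arm.* Controls have PEEP set by the High PEEP table and also carry the balloon. The synopsis trigger and the 7.2 list are not limited by arm. More losses in the intervention arm is a reasonable expectation, not a stated fact.
- *That follow-up stops at early completion.* Section 3.1 states 28-day follow-up. What is missing is a statement that it continues after early completion.
- *That the bias could approach the planned 2-day effect.* That rests wholly on assumed inputs.
- *That daily titration in 5.1 conflicts with the cap.* Section 5.1 is only silent on raising PEEP again after a reduction.

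**Conclusion.** The point holds as a conflict between stated rules and should be corrected. Section 7.2 and the synopsis give different consequences for the same hypotensive event. Refractory hypotension decides early completion and a DSMB suspension but is undefined. A patient capped below the PEEP giving Ptp 0 cannot satisfy both the cap and the intervention SBT rule. This last conflict is conditional on the cap lying below that level.

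The effect on the analysis is a possibility, not a finding. Early completion together with ignoring missing values could take treatment-related events out of the primary t-test, probably more often in the intervention arm but not exclusively. No section applies the 28-day follow-up of 3.1 after early completion, or says that such patients are analysed as randomised. With no event rate in the documents, neither the frequency of the conflict nor the size of any bias or loss of power can be given.

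**What to change.** 1. **Synopsis and 5.1:** state that 7.2 governs when its thresholds are met. Keep the clinical team's discretion to stop titration at any time for any PEEP-related change, and record the reason.
2. **5.1, intervention-group SBT:** add that a capped patient is tested at pressure support 5 cm H₂O and a PEEP no higher than the cap.
3. **4.4(c):** define refractory hypotension as the 7.2 parameter still unacceptable at the pre-intervention PEEP. Study titration then ends, and the patient is managed under the control-arm PEEP and SBT rules or by clinical judgement. Do not carry this definition into 7.3 as a restriction: the DSMB trigger should be no narrower than the CTCAE grade 3 to 5 hypotension listed in 7.2.
4. **4.4 and 6.2:** after any stop other than withdrawal of consent, in either arm, collect ventilator and vital status to day 28 and analyse the patient in the randomised group.

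The cost is a few sentences and one form field for the reason. The outcome already comes from the EMR. The downside is that some off-protocol patients stay in the analysis, which can dilute the estimated effect.

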4.3 Intervention procedures

All patients in both groups will have an esophageal balloon catheter inserted by a research investigator. The catheter will be inserted into their nare while upright (head of bed >30 degrees) to a depth slightly more than the estimated distance from the lower sternum to the back of the ear (typically around 60 cm). Gastric positioning will be confirmed with abdominal compression testing and the catheter then retracted 10 – 20cm into the lower esophagus. Placement will be confirmed with the presence of cardiac oscillations on the esophageal probe. The probe will then be secured to the patient's nasal opening using tape.

Pressures (Pes, Paw, and Ptp) are measured directly through the ventilator. Values of Paw, Pes, and Ptp will be collected daily in both groups.

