5.2 Other measurements

Variable	Source	How Measured	Baseline	Daily	Completion
Outcomes					
Ventilator free days at day 28 (Primary outcome)	EMR	Days alive and free of the ventilator			X
Reintubation	EMR	Intubated within 72 hours of extubation		X	X
ICU Length of Stay	EMR	Days			X
Hospital Length of Stay	EMR	Days			X
Tracheostomy	EMR	Y/N			X
Extubation prior to meeting established criteria	EMR	Y/N			X
Highest RASS	EMR	-5 to +4 (single highest value used)	X	X	
Lowest RASS	EMR	-5 to +4 (single lowest value used)	X	X	
Exposures					
Esophageal pressure (Pes)	Ventilator	cm H ₂ O	X	X	
Airway pressure (Paw)	Ventilator	cm H ₂ O	X	X	
Transpulmonary pressure (Ptp) (inspiratory and expiratory)	Ventilator	cm H ₂ O	X	X	
PEEP	Ventilator	cm H ₂ O	X	X	
Opioids	EMR	Continuous, bolus sch, bolus prn, oral sch, oral prn	X	X	
Propofol	EMR	Y/N	X	X	
Dexmedetomidine	EMR	Y/N	X	X	
Benzodiazepines	EMR	Continuous, bolus sch, bolus prn, oral sch, oral prn	X	X	
Antipsychotics	EMR	Sched, PRN	X	X	
Neuromuscular blockade	EMR	Y/N	X	X	
Corticosteroid use	EMR	Y/N	X	X	
Fluid Balance	EMR	Net fluid balance prior to extubation		X	
Safety Measures					
Vasopressor requirement	EMR	norepinephrine equivalents(9)	X	X	
Pneumothorax	EMR	Y/N	X	X	
Other Variables of Interest					
Age	EMR	Years	X		
Race/Ethnicity					
BMI	EMR	kg/m ²	X		
Partial Pressure of Oxygen (PaO ₂)	EMR	mmHg	X	X	
Oxygen Saturation (SpO ₂)	EMR	%	X	X	

PaO ₂ /FiO ₂ ratio	Calculated	Number	X	X	
SpO ₂ /FiO ₂ ratio	Calculated	Number	X	X	
Charlson Comorbidities	EMR	Y/N	X		
Waist circumference	EMR	cm	X		
CAM-ICU	EMR	Positive/Negative	X	X	
SOFA	EMR	Calculated	X		
COVID (y/n)	EMR	Y/N	X		

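### The adverse-event definition is a closed list of three event types that omits most of the balloon-placement risks the protocol itself names, in a trial where both arms receive the balloon

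*Combined protocol and SAP*

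**What the plan says.** Section 7.2 (Adverse Event Reporting) gives the operative definition: "All Adverse Events will be documented and graded using CTCAE grading, defined as any patient who develops one of the following". The list is "grade 3-5 hypotension", "grade 2-5 pneumothorax" and "grade 2-5 epistaxis". It contains no wording such as *including* or *for example*.

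Section 7.1 describes the risks of balloon placement as relatively small and gives them as "such as trauma to the nasopharynx, esophageal irritation, stimulation of cough or vomiting". A separate sentence there deals with ventilation: "Adverse events possibly related to mechanical ventilation and PEEP titration will be defined as new development of pneumothorax and hypotension".

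On exposure, section 4.3 states: "All patients in both groups will have an esophageal balloon catheter inserted by a research investigator". Pressures are then collected daily in both groups. Section 5.1 sets control PEEP from the High PEEP ARDSnet table.

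On collection and review, the rows under "Safety Measures" in Table 5.2 are vasopressor requirement and pneumothorax. Section 7.2 has possible adverse events screened daily and reviewed independently within 72 hours; those judged probably or definitely related to the intervention go to the IRB. Section 7.3 grades events for the DSMB by reference back to the 7.2 list, and its suspension triggers are pneumothorax, refractory hypotension and death.

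**The concern.** The protocol names specific harms of a study procedure and then defines adverse events so that most of them fall outside. This differs from a plan that leaves safety collection unspecified, because following the text exactly produces the omission.

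What is at stake is the safety record of the procedure, not the efficacy result. An episode of vomiting or esophageal irritation attributed to the balloon would have no defined place on the case report form, no independent review and no path to the DSMB. This matters most for the controls. Their PEEP does not depend on the balloon, so they carry its risk with no apparent treatment purpose. That last statement is an inference from sections 4.3 and 5.1, but a firm one.

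**Working it through.** No figure in the plan is in dispute, so the check is mainly a comparison of texts.

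**Step 1. Follow each risk named in 7.1 through the safety sections.**

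| Risk named in 7.1 | On the 7.2 list? | Row under Table 5.2 safety heading? | DSMB suspension trigger (7.3)? |
|---|---|---|---|
| Nasopharyngeal trauma | Only as epistaxis of grade 2 or higher | No | No |
| Esophageal irritation | No | No | No |
| Cough | No | No | No |
| Vomiting | No | No | No |

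Three of the four are wholly outside the definition and one is partly inside.

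**Step 2. Look for another route into the record.**

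- The daily screen and the independent review in 7.2 act on possible adverse events. The only general meaning the document gives that term is the three-item list.
- The DSMB grading in 7.3 points back to the same list. The DSMB also watches deaths, so the list is not everything monitored, but that does not bring in the four risks.
- The synopsis (Safety Evaluations) directs the DSMB to differences between groups in hypotension requiring vasopressors and in pneumothorax. A harm of a procedure done in both arms would be expected in both, so a difference between arms could miss it even if it were recorded.
- Section 4.4(c) refers to adverse effects with an open-ended list of examples. It governs when a participant leaves the study, not what is recorded or counted.

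**Step 3. Check whether relatedness review would reach controls.** IRB submission depends on relation to the intervention. Sections 1.2 and 4.3 describe balloon placement in both groups under headings about the intervention. The synopsis (Study Phases) puts balloon placement in a pre-intervention phase and reserves the intervention phase for PEEP titration in one group. The text therefore does not settle whether a control patient's balloon counts.

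**Step 4. Size of the exposed group.** Section 3.3 gives 38 per arm: 2 × 38 = 76 patients with a balloon, 38 of them controls.

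**Step 5. How many events might be missed.** The documents give no rate for the unlisted harms, so the rates p below are assumptions. Expected count = n × p. Chance of at least one event = 1 − (1 − p)^n.

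| Assumed rate | Expected in 76 | Expected in 38 controls | Chance of at least one in controls |
|---|---|---|---|
| 2% | 1.5 | 0.8 | 54% |
| 5% | 3.8 | 1.9 | 86% |
| 10% | 7.6 | 3.8 | 98% |
| 20% | 15.2 | 7.6 | >99.9% |

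These show scale only. They are not estimates for this population.

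**The case against.** The strongest reply is that a short, graded list is a sensible choice in critical illness. Most untoward events there come from the underlying disease, and cough or vomiting in sedated patients is hard to attribute to a catheter. The trial's objective is duration of ventilation, no endpoint claims to establish balloon safety, and patients are under continuous bedside monitoring. Section 4.4(c) is also open-ended, so a serious balloon complication could still end a patient's participation.

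Part of this stands. Attribution will be difficult, the primary analysis is untouched, and a targeted list is reasonable for background illness. It does not justify omitting named risks of a procedure done for the study. Bedside monitoring and an exit criterion do not create a count or a report to the DSMB.

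Several stronger readings are tempting and are not supported:

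- *All balloon harms are excluded.* Epistaxis of grade 2 or higher is documented and graded in both arms, and epistaxis needing intervention is a subject stopping rule. Its absence from Table 5.2 and from the suspension triggers does not mean it goes unrecorded.
- *The protocol names esophageal injury and then ignores it.* Section 7.1 names irritation, not injury.
- *The trial would report zero balloon events.* An event that is not collected has no count, which is different from a count of zero.
- *The omission can be sized by the bound for no events in 76 patients.* The bound 1 − 0.05^(1/76) = 3.9% is one-sided; the two-sided version is 1 − 0.025^(1/76) = 4.7%. Either describes what could be said if events were recorded and none occurred. Neither measures harm from the plan.

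**Conclusion.** The point holds as a cheap improvement. Section 7.2 read as written leaves three of the four balloon risks named in 7.1, and part of the fourth, outside recording, independent review and DSMB reporting. All 76 patients are exposed, including 38 controls for whom the balloon appears to serve measurement only. How many events would be missed cannot be known from the documents.

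The conclusion rests on two readings: that the 7.2 list is exhaustive, as its wording indicates, and that the term possible adverse events later in 7.2 takes its meaning from that list. The consequence is an incomplete safety record for a research procedure. The ventilator-free-day result and the comparison of hypotension and pneumothorax between arms are unaffected.

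**What to change.** 1. In 7.2, add to the definition events attributed to placement or presence of the balloon. Cover the risks named in 7.1, with a CTCAE grade threshold as for the existing items.
2. Add these events and epistaxis to the safety rows of Table 5.2.
3. Report them to the DSMB by arm and pooled. The pooled count is needed because a comparison between arms cannot show a harm common to both.
4. State in 7.2 that, for relatedness review, the intervention includes the balloon in control patients.
5. Reconcile the open-ended wording of 4.4(c) with the closed list in 7.2.

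The cost is a few extra fields on a daily screen that already exists and some more events for the independent reviewer. Attribution in sedated patients will be uncertain, and a grade threshold should limit the number of trivial reports. The sample size and the primary analysis do not change.
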